4.2 Method of assigning patients to treatment groups

[REDACTED], the Interactive Web Response System (IWRS) vendor, is responsible for generating the randomization code by computer software incorporating a random number generator. The allocation ratio is 1:1:1 (20-60 mg: 80-120 mg: placebo).

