15.1.3. PRIMARY ANALYSIS OF PRIMARY EFFICACY VARIABLE(S)

15.1.3.1. Montgomery-Asberg Depression Rating Scale (MADRS)

The primary efficacy variable is the change from baseline in the MADRS total score at Week 6 for testing superiority of SM-13496 (20-60 or 80-120 mg/day) to placebo, versus the null hypothesis of no difference versus placebo. The hypothesis for each SM-13496 treatment group will be considered independently.

Let μ_{20-60} , μ_{80-120} , and μ_{placebo} represent the mean changes from baseline in the MADRS total score at Week 6 in the 20-60mg, 80-120mg, and placebo groups, respectively. The following 2 hypotheses will be tested to compare the mean changes at Week 6 of each SM-13496 group with that of the placebo group:

- H01: $\mu_{20-60} = \mu_{\text{placebo}}$ versus the alternate H11: $\mu_{20-60} \neq \mu_{\text{placebo}}$.
- H02: $\mu_{80-120} = \mu_{\text{placebo}}$ versus the alternate H12: $\mu_{80-120} \neq \mu_{\text{placebo}}$.

The rater-administered MADRS data will be used for all statistical analyses.

The MMRM method will be used in the ITT population. The MMRM model will include treatment as a categorical factor, visit (Week 1, 2, 3, 4, 5, and 6; as a categorical variable), pooled center, the MADRS total score at baseline as a covariate, and the treatment-by-visit interaction. An unstructured covariance matrix will be used for the within-patient correlation and the Kenward-Rogers approximation will be used to calculate the denominator degree of freedom. In the case of a convergence problem with the unstructured covariance matrix, the following structures with robust sandwich estimator for the standard error of the fixed effect estimates will be assessed in a sequential fashion: heterogeneous Toeplitz, heterogeneous first-order autoregressive, and Toeplitz. Among these 3 covariance structures, the first structure yielding convergence will be used for the MMRM analysis. P-values for comparisons of primary efficacy variable at Week 6 between SM-13496 groups and the placebo group will be adjusted for multiplicity using a Hochberg procedure (section 7.4).

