APPENDIX 3. SAS CODE

Treatment: TRTPN
Analysis visit: AVISIT

1. Mixed Model Repeated Measures (MMRM) Analysis

Note: Ensure that input dataset is sorted by USUBJID AVISIT prior to initiating the MIXED procedure.

```
ods output estimates=outset /*Output from estimate statement*/  
diffs=outdiff /*Treatment Group Comparison*/  
R=outr /*R matrix */  
lsmeans=outlsmean; /*LSmeans of each treatment group*/
```

```
PROC MIXED;  
CLASS SUBJID POOLSITE TRTPN AVISIT;  
MODEL CFB = BASE POOLSITE TRTPN AVISIT TRTPN*AVISIT/DDFM=KR;  
REPEATED AVISIT /TYPE=UN SUBJECT=SUBJID R;  
LSMEANS TRTPN* AVISIT /PDIFF CL;  
ESTIMATE 'LINEAR TREND TEST FOR DOSE RESPONSE'  
TRTPN 0 1 -1 TRTPN*AVISIT 0 0 0 0 0 0 0 0 0 0 0 0 0 1  
0 0 0 0 0 0 -1/CL;  
ESTIMATE 'DOSE-RESPONSE 20-60 vs 80-120' TRTPN -1 1 0 TRTPN*AVISIT  
0 0 0 0 0 0 -1 0 0 0 0 0 0 1 0 0 0 0 0 0 0/CL;  
RUN;
```

a. Mixed Model Repeated Measures (MMRM) Analysis for the case above
model fails to converge

```
PROC MIXED empirical;
```

Document:	K:\DSP\SM-13496\KVA95374\Biostatistics\Documentation\SAP	Version Number:	1.0
Author:	[REDACTED]	Version Date:	30MAR2017

Template No: CS_TP_BS016 – Revision 3
Effective Date: 01May2012

Reference: CS_WI_BS005

Copyright © 2012 [REDACTED] All rights reserved.
The contents of this document are confidential and proprietary to [REDACTED]. Unauthorized use, disclosure or reproduction is strictly prohibited.

```
CLASS SUBJID POOLSITE TRTPN AVISIT;  
MODEL TOTCFB = TOTBL POOLSITE TRTPN AVISIT TRTPN*AVISIT;  
REPEATED AVISIT /TYPE=XXX SUBJECT=SUBJID R;  
LSMEANS TRTPN*AVISIT /PDIFF CL;  
ESTIMATE 'LINEAR TREND TEST FOR DOSE RESPONSE'  
TRTPN 0 1 -1 TRTPN*AVISIT 0 0 0 0 0 0 0 0 0 0 0 0 1  
0 0 0 0 0 0 -1/CL;  
ESTIMATE 'DOSE-RESPONSE 20 vs 80-160' TRTPN -1 1 0 TRTPN*  
AVISIT 0 0 0 0 0 0 -1 0 0 0 0 0 0 1 0 0 0 0 0 0/CL;  
RUN;
```

XXX: application order
Heterogeneous Toeplitz (TYPE=TOEPH)
Heterogeneous first-order autoregressive (TYPE=ARH(1))
Toeplitz (TYPE=TOEP)

2. Analysis of Covariance

```
PROC MIXED;  
CLASS TRTPN POOLSITE;  
MODEL CFB = TRTPN POOLSITE BASE;  
LSMEANS TRTPN / PDIFF CL;  
ESTIMATE 'LINEAR TREND' TRTPN 0 1 -1 /CL;  
ESTIMATE 'DOSE-RESPONSE 20 vs 80-160' TRTPN -1 1 0/CL;  
RUN;
```

3. Sensitivity Analysis

a. Random Effects Pattern Model

```
If TRT01PN=1 then DOSE1=1 else DOSE1=0;  
If TRT01PN=2 then DOSE2=1 else DOSE2=0;  
If COMPLFL="Y" then DROP=1 else DROP=0;
```

```
PROC MIXED;  
CLASS USUBJID;  
MODEL AVAL = QSDAY DOSE1 DOSE2 QSDAY*DOSE1 QSDAY*DOSE2  

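### The dose-response ESTIMATE statements in the SAP's MMRM code carry 21 or 20 treatment-by-visit coefficients for an 18-cell model, so as specified none targets Week 6

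*SAP*

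**What the plan says.** SAP section 15.1.3.1 defines the primary MMRM with a visit factor: "visit (Week 1, 2, 3, 4, 5, and 6; as a categorical variable". Protocol section 9.5.2 specifies the same visits. There are three arms; Protocol section 4.2 states: "The allocation ratio is 1:1:1 (20-60 mg: 80-120 mg: placebo".

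SAP Appendix 3, item 1 implements the model with "CLASS SUBJID POOLSITE TRTPN AVISIT" and "MODEL CFB = BASE POOLSITE TRTPN AVISIT TRTPN*AVISIT/DDFM=KR". The response is change from baseline and the baseline score is a covariate, so baseline is not a response visit.

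Two contrasts are attached. The first is labelled "ESTIMATE 'LINEAR TREND TEST FOR DOSE RESPONSE"; its first coefficient line is "TRTPN 0 1 -1 TRTPN*AVISIT 0 0 0 0 0 0 0 0 0 0 0 0 0 1", and a second line adds seven more values ending in -1. The second contrast begins "ESTIMATE 'DOSE-RESPONSE 20-60 vs 80-120' TRTPN -1 1 0 TRTPN*AVISIT" and continues "0 0 0 0 0 0 -1 0 0 0 0 0 0 1 0 0 0 0 0 0 0/CL".

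A fallback block, used if the unstructured covariance does not converge, repeats both contrasts with one coefficient fewer each. Its dose contrast is labelled 20 versus 80-160, although no arm goes above 120 mg. Both blocks also request all pairwise differences of the treatment-by-visit least-squares means.

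**The concern.** The number of interaction coefficients should equal the number of treatment-by-visit cells, and the non-zero values should sit on the Week 6 cells of the arms being compared. Neither holds for the model the SAP describes. The main code is laid out as 3 × 7 = 21. The fallback has 20, which is not a multiple of three and so fits no whole number of visits per arm.

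At stake is the dose-response output. Run as written on the specified model, these lines give either no estimate or, under a different visit coding, an estimate that in one case belongs to Week 5 but carries a dose-response label. Because the code is prespecified, a programmer may copy it without recounting.

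**Working it through.** **Inputs.** Three treatment levels (Protocol 4.2); six visit levels, Weeks 1 to 6 (SAP 15.1.3.1); CLASS order TRTPN then AVISIT (Appendix 3, item 1); the coefficient lists as printed there.

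**Cell count.** 3 × 6 = 18. With visit varying fastest, position p belongs to arm ⌈p/6⌉ and week ((p − 1) mod 6) + 1. Week 6 is therefore at positions 6, 12 and 18.

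**Counting the printed lists.**
- Main trend: 14 values on the first line + 7 on the second = 21.
- Main dose: 21.
- Fallback trend: 13 + 7 = 20.
- Fallback dose: 20.

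**Where the non-zero values land with six visits.**

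| Contrast | TRTPN part | Non-zero positions | Cells reached |
|---|---|---|---|
| Main trend | 0 1 -1 | +1 at 14, -1 at 21 | arm 3 Week 2; no cell |
| Main dose | -1 1 0 | -1 at 7, +1 at 14 | arm 2 Week 1; arm 3 Week 2 |
| Fallback trend | 0 1 -1 | +1 at 13, -1 at 20 | arm 3 Week 1; no cell |
| Fallback dose | -1 1 0 | -1 at 7, +1 at 14 | arm 2 Week 1; arm 3 Week 2 |

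None of positions 6, 12 or 18 is used.

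**Estimability by hand.** In this parameterisation the interaction coefficients within each arm must sum to that arm's TRTPN coefficient. Those across arms at each visit must sum to the AVISIT coefficient, which is 0 because none is given.
- Both dose contrasts: the arm 1 interaction sum is 0 but the TRTPN coefficient is -1. This fails.
- Both trend contrasts, with the surplus -1 dropped: the arm 2 sum is 0 against +1, and the arm 3 sum is +1 against -1. This fails.

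**Estimability by rank.** A design matrix was built with intercept, baseline, site, 3 arms, 6 visits and 18 cells. A contrast L is estimable if rank([X; L]) = rank(X). All four coded contrasts fail after truncation to 18 values. They also fail if treatment, rather than visit, is taken as the faster index.

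**Seven visit levels.** If AVISIT kept an extra level before Week 1, Week 6 would be at 7, 14 and 21, and Week 5 at 6, 13 and 20. With visit fastest, all four contrasts become estimable, whether that extra level is empty or filled. Both main contrasts (14 and 21; 7 and 14) and the fallback dose contrast (7 and 14) then fall on Week 6. The fallback trend (13 and 20) falls on Week 5.

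**Corrected vectors.** In arm order 20-60, 80-120, placebo:
- Dose, TRTPN -1 1 0, with -1 at cell 6 and +1 at cell 12: arm sums -1, +1, 0; Week 6 sum 0.
- Trend, TRTPN 0 1 -1, with +1 at cell 12 and -1 at cell 18: arm sums 0, +1, -1; Week 6 sum 0.

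Both pass the rank test.

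**Arm coding within Appendix 3.** The random-effects pattern mixture code (item 3a) makes treatment values 1 and 2 the doses. The multiple-imputation code (item 3b) treats 2 and 3 as active and uses 1 as the control. If placebo is level 1, followed by 20-60 and 80-120, the vectors above would estimate 20-60 minus placebo and 20-60 minus 80-120. Both are estimable, so nothing would flag the error.

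**The case against.** The strongest reply is that nothing of substance is lost. The least-squares means statement with pairwise differences already gives 20-60 versus 80-120 at Week 6. In the arm order the contrasts imply, the trend contrast is simply 80-120 minus placebo, which is one of the two primary comparisons. The SAP text on the primary analysis (15.1.3) and on multiplicity (7.4) describes no MMRM dose-response test; the contrasts exist only as appendix code. This stands and limits the point to a code correction. A reader might infer that the primary analysis is compromised, or that the only between-dose comparison is lost. The documents support neither.

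The second reply is that the regular 7+7+7 layout suggests a seven-level visit variable, and SAP Appendix 1 does list Baseline ahead of Week 1 among the visits for presentation. On that reading the main code works. This stands as a condition on the finding, but it does not clear the code. It contradicts the Weeks 1 to 6 model, and the imputation code in the same appendix creates visits 1 to 6 only. Appendix 1 also lists a Week 6 (LOCF) visit; if that were the seventh level, sorted last, positions 7, 14 and 21 would target the LOCF record. Even with Baseline first, the fallback trend misses Week 6.

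Third, a zero may have been lost from each fallback line when the PDF was read. That could explain 20 against 21, but not 21 against 18, since lost characters do not add coefficients.

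**Conclusion.** The mismatch is real: 21 and 20 coefficients against 18 cells. For the model as specified, all four contrasts miss Week 6 and are non-estimable. This rests on exactly six visit levels and on surplus coefficients being dropped. The documents do not say how the software treats surplus values; if it rejects the statement, there is still no estimate. A reader might take the contrasts to be broken whatever the data set looks like. That goes too far, because a seventh level sorted first would make three of them hit Week 6, though contrary to the text.

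The importance is small. The primary comparisons and their Hochberg adjustment do not use these lines, and the intended Week 6 differences are available from the pairwise least-squares means. What remains is a risk of missing or mislabelled supplementary output. The conflicting treatment coding could also turn a partial correction into a silent error.

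**What to change.** 1. Restrict AVISIT to Weeks 1 to 6 in the MMRM input and say so in Appendix 3.
2. State one TRTPN/TRT01PN coding for all of Appendix 3 and align items 3a and 3b with it. Check the ANCOVA contrasts in item 2 as well, since they use the same arm positions.
3. Use 18 interaction coefficients in both MMRM blocks. With order 20-60, 80-120, placebo:
   - Dose: TRTPN -1 1 0; interaction `0 0 0 0 0 -1  0 0 0 0 0 1  0 0 0 0 0 0`.
   - Trend: TRTPN 0 1 -1; interaction `0 0 0 0 0 0  0 0 0 0 0 1  0 0 0 0 0 -1`.
4. If placebo is level 1, followed by 20-60 and 80-120, permute the coefficients. Dose becomes TRTPN 0 -1 1 with -1 at cell 12 and +1 at cell 18; trend becomes TRTPN -1 0 1 with -1 at cell 6 and +1 at cell 18.
5. Correct the fallback label so that it names the arms of this trial.

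A simpler alternative is to delete the ESTIMATE lines and report the Week 6 differences from LSMEANS. Either way the cost is four statements of code and a line on coding, with no effect on data collection, sample size or the primary analysis.

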15.1.4.2. Random Effects Pattern Mixture Model

A random effects pattern mixture model (Hedeker & Gibbons, 1997) will be applied as one of two sensitivity analyses to explore the robustness of the MMRM results for the primary and key secondary efficacy variables for the ITT population.

Using a random effects PMM, one can examine (a) the degree to which the groups defined by the dropout patterns differ in terms of the outcome variable (i.e., main effect of the dropout pattern variable) and (b) the degree to which the dropout pattern moderates the influence of other model terms (i.e., interactions with the dropout pattern). In deciding on an appropriate grouping of the dropout patterns, an important consideration is the sparseness of the data for each pattern. If a pattern has very few observations, it may not make sense to treat it as a separate group in the analysis. About 82% of randomized patients in the present study were completers as of last patient last visit on 20FEB2017. Hedeker and Gibbons indicated that (Hedeker & Gibbons, 1997) if a large percentage of patients complete the study, it is reasonable to classify patients into completers and dropouts.

Prior to selecting the completer/dropout pattern used above, exploratory analyses were conducted using data from previous SM-13496 schizophrenia studies (D1050229 and D1050233). The completion rates for these schizophrenia studies were 66% for Study D1050229, and 72% for Study D1050233, respectively. The drop out rate for D1002001 is 17.4%. These exploratory analyses involved the following sets of dropout patterns: 1) dropouts and completers, 2) early dropouts, late dropouts, and completers; and, 3) dropouts due to insufficient clinical response and AEs, dropouts due to other reasons, and completers. The overall conclusions from these exploratory analyses were consistent with those from the primary efficacy analyses from the respective studies.

The random effects pattern mixture model will include fixed terms for treatment, time (as a continuous variable), dropout pattern, and two-way interaction terms (i.e., treatment-by-time, dropout pattern-by-treatment, dropout pattern-by-time), and a three-way interaction term (dropout pattern-by-treatment-by-time). The model will also include subject-specific random effects for intercept and time. The response

Document: K:\DSP\SM-13496\KVA95374\Biostatistics\Documentation\SAP

Author:

Version Number:

1.0

Version Date:

30MAR2017

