Template No: CS_TP_BS016 – Revision 3

Reference: CS_WI_BS005

Effective Date: 01May2012

Copyright © 2012 [REDACTED] All rights reserved.

The contents of this document are confidential and proprietary to [REDACTED]. Unauthorized use, disclosure or reproduction is strictly prohibited.

variables will be the observed values of the efficacy variables over time, including the baseline value. Patients will be classified into two separate patterns: dropouts and completers. To illustrate, only two treatment groups are considered. Let y_{ij} represent the response value of the i th subject at time j (i.e., actual day of assessment), the following random effects pattern mixture model with an unstructured covariance matrix is fitted:

$$y_{ij} = \beta_0 + \beta_1 Time_{ij} + \beta_2 Treat_i + \beta_3 (Treat_i \times Time_{ij}) + \beta_4 Drop_i + \beta_5 (Drop_i \times Time_{ij}) + \beta_6 (Drop_i \times Treat_i) + \beta_7 (Drop_i \times Treat_i \times Time_{ij}) + v_{0i} + v_{1i} Time_{ij} + \epsilon_{ij} \quad (1)$$

Where:

Drop = 0 for completers, and 1 for dropouts

Treat = 0 for patients in the placebo group, and 1 for patients in the SM-13496 treatment group

The random intercept v_{0i} and random time effect v_{1i} are assumed to follow a bivariate normal distribution, and the model residuals ϵ_{ij} are assumed to be independently distributed and follow a univariate normal distribution.

Based on the above specified random effects pattern mixture model, the parameter estimates for fixed effects (intercept, time, treatment, treatment-by-time, dropout pattern, dropout pattern-by-time, dropout pattern-by-treatment, and dropout pattern-by-treatment-by-time) as well as the covariance matrix for the parameter estimates will be obtained by using the SAS PROC MIXED procedure.

Substituting Drop = 0 and 1 in the above random effects pattern mixture model (1), the following regression models for completers and dropouts can be obtained. The model for completers is:

$$y_{ij} = \beta_0 + \beta_1 Time_{ij} + \beta_2 Treat_i + \beta_3 (Treat_i \times Time_{ij}) + v_{0i} + v_{1i} Time_{ij} + \epsilon_{ij} \quad (2)$$

and the model for dropouts is:

$$y_{ij} = (\beta_0 + \beta_4) + (\beta_1 + \beta_5) Time_{ij} + (\beta_2 + \beta_6) Treat_i + (\beta_3 + \beta_7) (Treat_i \times Time_{ij}) + v_{0i} + v_{1i} Time_{ij} + \epsilon_{ij} \quad (3)$$

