Finally, the overall parameter estimates from the random effects pattern mixture model will be compared with the estimates from a random effects model that does not include dropout pattern, but will include fixed terms for treatment, time (as a continuous variable), and a treatment-by-time interaction. This model will also include subject-specific random effects for intercept and time. The random effect model is:

$$y_{ij} = \beta_0 + \beta_1 Time_{ij} + \beta_2 Treat_i + \beta_3 (Treat_i \times Time_{ij}) + v_{oi} + v_{1i} Time_{ij} + \epsilon_{ij} \quad (6)$$

A comparison of the parameters between the above two models helps to assess any impact of missingness (Siddiqui, Hung, & O'Neil, 2009). If the results from these two models are consistent, it implies the MAR assumption is reasonable, because the random effects model without dropout pattern assumes MAR, which is the same assumption that MMRM requires.

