DROP DROP*QSDAY DROP*DOSE1 DROP*DOSE2  
DROP*DOSE1*QSDAY DROP*DOSE2*QSDAY / SOLUTION COVB  
DDFM=KR;  
RANDOM INTERCEPT DAY/SUB=USUBKID TYPE=UN G;  
RUN;
```

```
PROC IML;  
USE VCOV1;  
READ all into vcovm;  
USE estb;  
READ all into estbm;
```

```
MEANV = ESTBM[,1];
```

Document: K:\DSP\SM-13496\KVA95374\Biostatistics\Documentation\SAP

Author: [REDACTED]

Version Number:

1.0

Version Date:

30MAR2017

Template No: CS_TP_BS016 - Revision 3

Reference: CS_WI_BS005

Effective Date: 01May2012

Copyright © 2012 [REDACTED] All rights reserved

The contents of this document are confidential and proprietary to [REDACTED]
reproduction is strictly prohibited.

Unauthorized use, disclosure or

```
VARB = VCOVM[1:12,1:12];
A = { 1 0 0 0 0 0 0 0 0 0 0 0, /* Completer - control intercept */
      0 1 0 0 0 0 0 0 0 0 0 0, /* Completer - control slope */
      0 0 1 0 0 0 0 0 0 0 0 0, /* Completer - dose1 intercept diff */
      0 0 0 1 0 0 0 0 0 0 0 0, /* Completer - dose2 intercept diff */
      0 0 0 0 1 0 0 0 0 0 0 0, /* Completer - dose1 slope diff */
      0 0 0 0 0 1 0 0 0 0 0 0, /* Completer - dose2 slope diff */

      1 0 0 0 0 0 1 0 0 0 0 0, /* Dropout - control intercept */
      0 1 0 0 0 0 0 1 0 0 0 0, /* Dropout - control slope */
      0 0 1 0 0 0 0 0 1 0 0 0, /* Dropout - dose1 intercept diff */
      0 0 0 1 0 0 0 0 0 1 0 0, /* Dropout - dose2 intercept diff */
      0 0 0 0 1 0 0 0 0 0 1 0, /* Dropout - dose1 slope diff */
      0 0 0 0 0 1 0 0 0 0 0 1 }; /* Dropout - dose2 slope diff */

meancd = A*meanv;
varccd = A*varb*T(A);

*COMPLETERS;
meanc = meancd[1:6,];
serrc = sqrt(vecdiag(varccd[1:6,1:6]));
zvalc = meanc/serrc;
lowec=meanc-1.96*serrc;
uppec=meanc+1.96*serrc;
probc = 2*(1-PROBNORM(abs(zvalc)));

**DROPOUTS;
meand = meancd[7:12,];
serrd = sqrt(vecdiag(varccd[7:12,7:12]));
zvald = meand/serrd;
lowed=meand-1.96*serrd;
upped=meand+1.96*serrd;
probd = 2*(1-PROBNORM(abs(zvald)));

/* indicator matrix to average over 2 patterns */
B = { 1 0 0 0 0 0 1 0 0 0 0 0,
      0 1 0 0 0 0 0 1 0 0 0 0,
      0 0 1 0 0 0 0 0 1 0 0 0,
      0 0 0 1 0 0 0 0 0 1 0 0,
      0 0 0 0 1 0 0 0 0 0 1 0,
      0 0 0 0 0 1 0 0 0 0 0 1 };

/* derivative matrix for average with respect to proportion
   (for application of delta method) */
C = { 1 0 0 0 0 0 -1 0 0 0 0 0,
      0 1 0 0 0 0 0 -1 0 0 0 0,
      0 0 1 0 0 0 0 0 -1 0 0 0,
      0 0 0 1 0 0 0 0 0 -1 0 0,
      0 0 0 0 1 0 0 0 0 0 -1 0,
      0 0 0 0 0 1 0 0 0 0 0 -1 };

propcd = J(12,12,0);
```

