Document: K:\DSP\SM-13496\KVA95374\Biostatistics\Documentation\SAP
Author: [REDACTED] Version Number: 1.0
Version Date: 30MAR2017

Template No: CS_TP_BS016 – Revision 3 Reference: CS_WI_BS005
Effective Date: 01May2012

Copyright © 2012 [REDACTED] All rights reserved. [REDACTED] Unauthorized use, disclosure or reproduction is strictly prohibited.

```
propcd[1,1] = &grp11/(&grp11+&grp21); /* Completer - control intercept
*/
propcd[2,2] = &grp11/(&grp11+&grp21); /* Completer - control slope
*/
propcd[3,3] = &grp12/(&grp12+&grp22); /* Completer - dose1 intercept
diff */
propcd[4,4] = &grp13/(&grp13+&grp23); /* Completer - dose2 intercept
diff */
propcd[5,5] = &grp12/(&grp12+&grp22); /* Completer - dose1 slope
diff */
propcd[6,6] = &grp13/(&grp13+&grp23); /* Completer - dose2 slope
diff */

propcd[7,7] = &grp21/(&grp11+&grp21); /* Dropout - control
intercept */
propcd[8,8] = &grp21/(&grp11+&grp21); /* Dropout - control slope
*/
propcd[9,9] = &grp22/(&grp12+&grp22); /* Dropout - dose1
intercept diff */
propcd[10,10] = &grp23/(&grp13+&grp23); /* Dropout - dose2
intercept diff */
propcd[11,11] = &grp22/(&grp12+&grp22); /* Dropout - dose1 slope
diff */
propcd[12,12] = &grp23/(&grp13+&grp23); /* Dropout - dose2 slope
diff */

propcdd = J(6,6,0);
propcdd[1,1] = &grp11*&grp21/((&grp11+&grp21)**3);
propcdd[2,2] = &grp11*&grp21/((&grp11+&grp21)**3);
propcdd[3,3] = &grp12*&grp22/((&grp12+&grp22)**3);
propcdd[4,4] = &grp13*&grp23/((&grp13+&grp23)**3);
propcdd[5,5] = &grp12*&grp22/((&grp12+&grp22)**3);
propcdd[6,6] = &grp13*&grp23/((&grp13+&grp23)**3);

meanpm = B*propcd*meancd;
varcpm = B*propcd*varccd*propcd*T(B)
+ propcdd*C*meancd*T(meancd)*T(C);
serrpm = sqrt(vecdiag(varcpm));
zvalpm = meanpm/serrpm;
lowepm=meanpm-1.96*serrpm;
uppepm=meanpm+1.96*serrpm;
probp = 2*(1-PROBNORM(abs(zvalpm)));

CREATE outdata var {meanc serrc lowec uppec probc meand serrd lowed upped
probd meanpm serrpm lowepm uppepm probpm};
append;
close outdata;

QUIT;

*Model repeated without drop out pattern:

PROC MIXED;
CLASS USUBJID;
MODEL AVAL = QSDAY DOSE1 DOSE2 DAY*DOSE1 DAY*DOSE2 /
```

Document: K:\DSP\SM-13496\KVA95374\Biostatistics\Documentation\SAP

Author:

Version Number:

1.0

Version Date:

30MAR2017

Template No: CS_TP_BS016 - Revision 3

Reference: CS_WI_BS005

Effective Date: 01May2012

Copyright © 2012 All rights reserved.

The contents of this document are confidential and proprietary to

Unauthorized use, disclosure or reproduction is strictly prohibited.

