SOLUTION COVB DDFM = KR;
RANDOM INTERCEPT DAY /SUB=USUBJID TYPE=UN G;
RUN;

b. Multiple Imputation

NOTE: Placebo based imputation

```
PROC MI
VAR SITEGR1N SCORE_1 SCORE_2 SCORE_3 SCORE_4 SCORE_5 SCORE_6
SCORE_7;
BY TRT01PN;
MCMC CHAIN=MULTIPLE IMPUTE=MONOTONE;
RUN;

%MACRO MI_IMP(INDATA=, ANVIS=, SEED=, VAR1=, VAR2=, OUTDATA=);
DATA EFF_MONO_IMP EFF_MONO_REST;
SET &INDATA;
IF TRT01PN IN (2,3) AND LASTVIS >=&ANVIS THEN OUTPUT
EFF_MONO_REST;
ELSE OUTPUT EFF_MONO_IMP;
RUN;

PROC SORT DATA= EFF_MONO_IMP;
BY _IMPUTATION_;
RUN;

PROC MI DATA=EFF_MONO_IMP OUT=EFF_REG_IMP NIMPUTE=1 SEED=&SEED
MINIMUM=0 MAXIMUM=60;
VAR &VAR1 &VAR2;
BY _IMPUTATION_;
MONOTONE REGRESSION(&VAR2= &VAR1 / DETAILS);
RUN;

DATA &OUTDATA;
SET EFF_MONO_REST EFF_REG_IMP;
RUN;

PROC DATASETS;
DELETE EFF_MONO_IMP EFF_MONO_REST EFF_REG_IMP;
RUN;
%MEND MI_IMP;
```

Document: K:\DSP\SM-13496\KVA95374\Biostatistics\Documentation\SAP
Author: [REDACTED] Version Number: 1.0
Version Date: 30MAR2017

Template No: CS_TP_BS016 – Revision 3
Effective Date: 01May2012

Reference: CS_WI_BS005

Copyright © 2012 [REDACTED] All rights reserved.
The contents of this document are confidential and proprietary to [REDACTED]. Unauthorized use, disclosure or reproduction is strictly prohibited.

```
%MI_IMP(INDATA=EFF_MONO, ANVIS=2, SEED=445566, VAR1=SCORE_1 SCORE_2,  
VAR2=SCORE_3, OUTDATA=EFF_IMP1);  
%MI_IMP(INDATA=EFF_IMP1, ANVIS=3, SEED=445566, VAR1=SCORE_1 SCORE_2  
SCORE_3, VAR2=SCORE_4, OUTDATA=EFF_IMP2);  
%MI_IMP(INDATA=EFF_IMP2, ANVIS=4, SEED=445566, VAR1=SCORE_1 SCORE_2  
SCORE_3 SCORE_4, VAR2=SCORE_5, OUTDATA=EFF_IMP3);  
%MI_IMP(INDATA=EFF_IMP3, ANVIS=5, SEED=445566, VAR1=SCORE_1 SCORE_2  
SCORE_3 SCORE_4 SCORE_5, VAR2=SCORE_6, OUTDATA=EFF_IMP4);  
%MI_IMP(INDATA=EFF_IMP4, ANVIS=6, SEED=445566, VAR1=SCORE_1 SCORE_2  
SCORE_3 SCORE_4 SCORE_5 SCORE_6, VAR2=SCORE_7, OUTDATA=EFF_IMP5);
```

```
DATA MI_EFF;  
  SET EFF_IMP5;  
  AVISITN=1;  
  DIFF=SCORE_2-SCORE_1;  
  OUTPUT;  
  AVISITN=2;  
  DIFF=SCORE_3-SCORE_1;  
  OUTPUT;  
  AVISITN=3;  
  DIFF=SCORE_4-SCORE_1;  
  OUTPUT;  
  AVISITN=4;  
  DIFF=SCORE_5-SCORE_1;  
  OUTPUT;  
  AVISITN=5;  
  DIFF=SCORE_6-SCORE_1;  
  OUTPUT;  
  AVISITN=6;  
  DIFF=SCORE_7-SCORE_1;  
  OUTPUT;
```

```
RUN;
```

```
ods listing close;
```

```
PROC MIXED;
```

```
  CLASS USUBJID TRT01PN AVISITN SITEGR1N;  
  MODEL      DIFF=SCORE_1      TRT01PN      AVISITN      SITEGR1N  
TR01PN*AVISITN/DDFM=KR SOLUTION CL;  
  REPEATED AVISITN /SUBJECT=USUBJID TYPE=UN;
```

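### SAP Appendix 3 reverses the dropout flag defined in Section 15.1.4.2, so the pattern mixture model would report completers and dropouts under each other's labels

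*SAP*

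**What the plan says.** SAP Section 15.1.4.2 specifies a random effects pattern mixture model for the primary and key secondary variables, with two patterns. The text sets "Drop = 0 for completers, and 1 for dropouts". Models (2) and (3) follow from that: the completer model uses the base coefficients alone, and the dropout model adds the Drop terms. Equation (4) then averages the two patterns, weighted by the proportions of completers and dropouts in the relevant arm. The overall result is compared with model (6), which has no dropout pattern, and the section concludes: "If the results from these two models are consistent, it implies the MAR assumption is reasonable". It also gives the dropout rate, in per cent: "The drop out rate for D1002001 is 17.4".

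SAP Appendix 3, item 3a, codes the flag as "If COMPLFL='Y' then DROP=1 else DROP=0". In the PROC IML step, row 1 of matrix A, which picks the base intercept, carries the comment "Completer - control intercept". Rows 1 to 6 are all commented as completers and rows 7 to 12 as dropouts. The first weight is written "propcd[1,1] = &grp11/(&grp11+&grp21); /* Completer - control intercept". The SAP does not say what &grp11 to &grp23 count.

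**The concern.** The text and the code give the same flag opposite meanings, and nothing later in the code reverses it back. Nothing in the SAP says which of the two takes precedence.

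Two things are at stake. First, one purpose of the model is to show how the dropout groups differ, and swapped labels would misdescribe how dropouts fared. Second, the SAP judges the missing-at-random assumption by comparing the overall estimate with model (6). If that estimate is mis-weighted, a discrepancy could appear or disappear for reasons unrelated to the data.

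A reversed 0/1 flag is also hard to detect. The model fit is identical and SAS gives no message. The delta-method term gives no warning either, because it is symmetric in the two counts.

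**Working it through.** **1. Which coefficients are which.** DROP is not in the CLASS statement, so it enters as a number. The MODEL statement lists the intercept, day, two dose terms and two day-by-dose terms, followed by the same six multiplied by DROP. Matrix A matches this order.

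| Rows of A | Coefficients | Group under the Section 15.1.4.2 coding | Group under the Appendix 3 coding | Label in the code |
|---|---|---|---|---|
| 1-6 | base (DROP=0) | completers | dropouts | Completer |
| 7-12 | base + DROP terms (DROP=1) | dropouts | completers | Dropout |

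The labels are right under the text's coding and wrong under the code's. This takes COMPLFL = Y to mean that the patient completed. The SAP does not define the flag, but no other reading is sensible.

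**2. Numerical check of the swap.** The model was fitted to simulated data under both codings, using the SAP's own matrices. Assumptions: 175 patients per arm, 30 of them dropouts, and different slopes by pattern. The coefficients were identical with the two blocks exchanged. For example, the fitted dose-1 slope difference per day was -0.0767 in true completers and 0.1283 in true dropouts. The code reports 0.1283 as completers and -0.0767 as dropouts.

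**3. Overall estimate if &grp1x are completer counts.** Inputs: dropout share d = 0.174 (Section 15.1.4.2) and completer share c = 1 - 0.174 = 0.826. Let x be the completer effect and e the dropout effect.

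- Intended: c·x + d·e
- Coded: d·x + c·e
- Shift (coded minus intended): (c - d)(e - x) = 0.652 (e - x)

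Take x = -3.5, borrowing the planning difference in protocol Section 3.5. The values of e are assumptions, because the documents give none.

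| e | Intended | Coded | Shift |
|---|---|---|---|
| -3.5 | -3.50 | -3.50 | 0 |
| -2 | 0.826(-3.5) + 0.174(-2) = -3.24 | 0.174(-3.5) + 0.826(-2) = -2.26 | +0.98 |
| 0 | -2.89 | -0.61 | +2.28 |
| +1 | -2.72 | +0.22 | +2.93 |

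**4. Precision, same condition.** The small pattern would carry 0.826 of the weight. With 167 per arm (protocol Section 3.5), 167 × 0.174 ≈ 29 dropouts and 138 completers. If dropouts had full follow-up, the ratio of coded to intended SE would be

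sqrt[(0.826²/29 + 0.174²/138) / (0.826²/138 + 0.174²/29)] = sqrt(0.02375/0.00599) = 1.99.

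Dropouts contribute fewer visits, so the ratio is higher in practice. For the 6-week effect it was 2.43, 2.60 and 2.76 at residual SDs of 3, 4 and 5. This assumes an SD of 6-week change of 10, a random-intercept SD of 4, and dropouts spread evenly over one to five post-baseline visits.

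**5. Overall estimate if the counts are tabulated by DROP, zero first.** Each pattern then receives its own weight. In the simulation the overall dose-1 slope difference was -0.0415 (SE 0.0192), the same as under the text's coding. With completer counts in &grp1x it became +0.0932 (SE 0.0642).

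**The case against.** The strongest reply is that the block is unfinished template code that cannot run as printed. The flag line has no semicolon before ELSE. The RANDOM statement reads "RANDOM INTERCEPT DAY/SUB=USUBKID TYPE=UN G", with a misspelled subject variable and a different time variable from the MODEL statement. Two input datasets are read but never created. A programmer must therefore edit the block, and Section 15.1.4.2 gives the coding unambiguously. This is fair as far as it goes, but adding a semicolon does not reverse the flag, and the errors SAS reports are not the one that matters here.

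Three further points stand as limits on the size:

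- The comments beside the weights name the parameter row. They suggest completer counts but do not prove that &grp11 holds one, so the mis-weighting is possible rather than established. Without it, the comparison with model (6) is unaffected.
- The code reports separate intercept and slope terms, not a 6-week effect. The effects in step 3 and the SE ratios in step 4 are illustrations.
- The 17.4% is given alongside figures for randomized patients, whereas the model uses the ITT population and arm-specific weights. The factor 0.652 is therefore approximate; at the SAP's rounded 82% completers it is 0.64.

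**Conclusion.** The concern holds. Appendix 3 contradicts Section 15.1.4.2, and following the code swaps the completer and dropout results, however the counts are defined.

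Mis-weighting of the overall estimate depends on &grp1x being completer counts. In that case the shift is about 0.65 times the gap between dropout and completer effects. It is zero if the effects are equal and more than 2 MADRS points in the illustration with no effect in dropouts. The SE of a 6-week effect would rise about 2.0 to 2.8 times under the stated assumptions, even with no shift.

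The scope is this one sensitivity analysis of the primary and key secondary variables. The primary MMRM, the Hochberg decision, the LOCF ANCOVA, the placebo-based imputation and the per-protocol MMRM do not use DROP. The point should be fixed, but it does not threaten the primary conclusion.

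**What to change.** In Appendix 3, item 3a:

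- Replace the flag line with `if COMPLFL='Y' then DROP=0; else DROP=1;`.
- Define &grp11 to &grp13 as completer counts and &grp21 to &grp23 as dropout counts, by arm (control, dose 1, dose 2).
- Use one time variable throughout (QSDAY or DAY), and USUBJID as the subject identifier.
- Settle one TRT01PN coding. Item 3a takes values 1 and 2 as the active doses, whereas item 3b takes 2 and 3 ("IF TRT01PN IN (2,3) AND LASTVIS >=&ANVIS THEN OUTPUT") with 1 as control. If 3b is right, DOSE1 in 3a flags placebo patients, again without an error message.

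The cost is a few lines in one code block, made before unblinding. No data, design or primary-analysis change is needed.
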